1.2 Study Design

This was a prospective, multi-center, single-arm study for NEUWAVE Flex Microwave Ablation System in the ablation of soft tissue lesions of the lung for medically inoperable subjects, or those who elect not to have surgery. Prospective subjects were informed about the nature of the research, given the informed consent form (ICF) to read, and given the opportunity to ask any questions about the study. Once the subject understood the content of the ICF, s/he was asked to provide written consent. Individuals scheduled for microwave ablation of the lung were to be enrolled after providing informed consent and meeting study entry criteria, known as the inclusion and exclusion criteria. Subjects were to be followed for approximately 1 year following the first ablation procedure for safety and effectiveness outcomes.

2 Treatment Assignment

This was a single-arm study where all enrolled subjects underwent transbronchial microwave ablation with the NeuWave Flex Microwave Ablation System.

3 Randomization and Blinding Procedures

This was a single-arm, open-label study. No randomization occurred and no blinding procedures were required.

4 Interval Windows

Interval windows are not defined for the purpose of analysis in this study outside of the visit windows that are provided in the Schedule of Assessments in Table 1 of the final protocol. There will be no assigning of observations to time points outside of the visit to which they are recorded in the electronic Case Report Forms (eCRFs). Data collected in Unscheduled Visit forms will be listed as such.

5 Levels of Significance

No hypotheses are specified for this study and no p-values are being calculated. Therefore, no level of significance is specified. All estimation of endpoints will be performed using 95% confidence intervals.

6 Analysis Sets

The study protocol identified two analysis sets:

- The Full Analysis Set (FAS) will consist of all subjects who are enrolled in the study and receive ablation through the flexible probe. The FAS was planned to be the primary analysis set for safety and effectiveness endpoints.
- The Per Protocol (PP) Analysis Set will consist of all subjects who are enrolled in the study and receive ablation through the flexible probe and have no major protocol deviations. Effectiveness analyses were planned to be repeated for the Per Protocol Set.

Given the decision to stop study enrollment at 10 subjects, only the Full Analysis Set will be defined for summarizing effectiveness and safety data in this study. A Per Protocol Analysis Set will not be defined.

7 Sample Size Justification

No formal hypotheses were planned to be tested in this study, and hence, a target sample size of 40 subjects (with an approximate equal distribution of device use by interventional pulmonologists and thoracic surgeons) was deemed adequate for a preliminary investigation of the feasibility of this procedure, as well as for providing sufficient information for appropriately sizing a subsequent study.

From a safety perspective, the AEs of interest in this study included: pneumothorax (requiring tube drainage), hemorrhage (bleeding requiring medical intervention), post-ablation syndrome, pain, pleural effusion (requiring tube drainage), infection, pneumonia, abscess, and bronchopleural fistula. A target sample size of 40 subjects provided a high likelihood of observing events in this composite and would allow for an initial evaluation of the frequency of occurrence relative to published literature in similar procedures.

As stated earlier, enrollment was stopped after 10 subjects received ablation and the original planned target of 40 subjects was not achieved.

8 Data Safety Monitoring Board

A DSMB was appointed by the Sponsor to review, on a regular basis, safety data from the study. The DSMB was to advise the Sponsor regarding the continuing safety of subjects and those yet to

be recruited to the study. Based on accumulating data from the study, the DSMB was to recommend whether to continue, suspend, modify, or stop the study. The composition, responsibilities, frequency of DSMB meetings, handling of emergency situations, and documentation of DSMB meetings was specified in the DSMB Charter and proceedings from DSMB meetings are maintained with the Sponsor.

9 Analyses to be Conducted

9.1 General Conventions

Subject data will be summarized using listings and tables. All eCRF data will be listed per subject for all subjects. Descriptive statistical analyses will be provided for pre-specified study endpoints. Summaries for continuous variables will include number of observations (n), mean, standard deviation, median, minimum, and maximum. Summaries for categorical variables will include number and percentage.

Analyses will be conducted using SAS software version 9.4 or higher. During the course of analysis programming of tables that are mocked up in this SAP, minor modifications may become necessary. Examples of these minor modifications include, but are not limited to, re-wording of a footnote, addition of a footnote, re-labeling of a column, or addition or removal of a column from a listing. In cases where modifications to tables or listings are not related to a change in statistical analysis methodology or conclusions that could be made on the originally proposed methodology, then no amendment of the SAP is necessary. Any final analyses that differ from what has been specified in this document will be identified within the final statistical output and documented within the clinical study report.

9.2 Disposition of Study Subjects

Subject disposition will be summarized in total using counts and percentages. The number and percentage of subjects completed and discontinued will be tabulated along with the specific reasons for discontinuation.

9.3 Demographic, Baseline, and Subject Health Status Characteristics

Summary statistics of subject demographics and baseline characteristics (age, gender, childbearing potential, race, ethnicity, and body mass index) will be presented in total for the Full Analysis Set. Subject medical history will be summarized by Medical Dictionary for Regulatory Activities (MedDRA) system organ class and preferred term.

9.4 Primary Endpoint Analyses

Device user experience feedback was collected from the treating physician who were to complete the User Experience Survey following each ablation procedure. The questionnaire was focused on procedure workflow and the user's assessment on ease/difficulty of using the device. Per the study

protocol, summary statistics were to be provided for each question in the survey; however, given the overall reduced sample size, only responses to the Probe Placement, Ablation Procedure, and General System Feedback sections will be summarized. All data collected on the User Experience Survey will be listed.

The number and percentage of subjects achieving technical success will be summarized and an exact 95% confidence interval will be presented. A similar summary will be presented for technique efficacy.

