6.0 ENDPOINTS

6.1 Primary Endpoints

The primary endpoints include the following:

- Device user experience: The data will come from the User Experience Survey, which will be completed by the treating physician following each ablation procedure.
- Technical success, defined as: ablation of the target lesion according to the protocol and covered completely, with an adequate margin, as defined by the performing physician (that is, the ablation zone completely overlaps or encompasses the target lesion plus an ablative margin), as assessed by cone beam CT imaging, immediately following the procedure.
- Technique efficacy, defined as ablation of the target lesion according to the protocol and covered completely, with an adequate margin, as defined by the performing physician (that is, the ablation zone completely overlaps or encompasses the target lesion plus and ablative margin). Technique efficacy will be assessed using CT imaging at Visit 3, which is 30 days \pm 7 days after the first ablation procedure.

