10.9 Analyses to be Conducted

Analyses described below will be performed on the pooled set of 40 patients [REDACTED]

Disposition of Study Patients

Patient disposition will be summarized using counts and percentages. The number and percentage of patients completed and discontinued along with the specific reasons for discontinuation will be tabulated by treatment group and in total.

Demographic and Baseline Characteristics

Summary statistics will be provided for patient demographics and pre-operative ablation characteristics.

Primary and Secondary Endpoint Analyses

Device user experience feedback will be collected from the treating physician who will complete the User Experience Survey following each ablation procedure. The questionnaire will focus on procedure workflow and the user's assessment on ease/difficulty of using the device. Summary statistics will be provided for each question.

The number and percentage of patients achieving technical success will be summarized and a 95% confidence interval will be estimated. Technique efficacy, as well as primary and secondary efficacy rates and hospital readmission rates, will be summarized in a similar manner. Local soft tissue lesion recurrence rates will be estimated using the Kaplan-Meier method and 95% confidence intervals will be provided.

The number and percentage of patients experiencing AEs from the start of ablation (Visit 2A) to Visit 3 (the first post-ablation visit) will be summarized by MedDRA preferred term and system organ class. A similar summary will also be provided for device related and procedure related, and all SAEs. Ninety-five percent confidence intervals may be provided for pre-specified adverse events of interest [REDACTED]

[REDACTED]

[REDACTED]

[REDACTED]

[REDACTED]

[REDACTED]

[REDACTED]

[REDACTED]

[REDACTED]

[REDACTED]

[REDACTED]

Similar summaries will also be provided for the entire observation period from the ablation procedure date through 1 year of follow-up.

The EORTC QOL questionnaires and Numeric Pain Rating Scale scores will be summarized with methodology consistent to the recommendations of the specific survey. Additional endpoints will be summarized with descriptive statistics.

Plans for Interim Analysis

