The original study protocol planned to continue study enrollment until 40 subjects were ablated (approximately 20 subjects ablated by interventional pulmonologists and 20 subjects ablated by thoracic surgeons) and completed Visit 3 (30 days \pm 7 days after the first ablation procedure). However, study enrollment was temporarily halted after 10 subjects were enrolled to convene a meeting of the Data Safety Monitoring Board (DSMB) following the death of one subject. While the DSMB recommended that the study could continue enrollment, the decision was made to permanently stop study enrollment and follow the 10 previously-enrolled subjects through the end of the study follow-up period of 1 year post-ablation. As such, this decision impacts several of the analyses originally planned in the study protocol and those changes will be identified in the appropriate sections throughout this SAP.

1 Study Overview

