9.7 Additional Endpoint Analyses

Counts and percentages will be provided for subject performance status as measured by the Eastern Cooperative Oncology Group (ECOG) classification at each visit. Summary statistics will be provided for the numeric pain rating scale measurement and hematology parameters at each visit. Pulmonary function tests will be summarized with summary statistics at each visit where they are measured and the change from the Screening visit measurement will also be summarized. Responses to each question of the EORTC QLQ-LC 13 will be summarized at each visit where the questionnaire was administered. Responses to the EORTC QLQ-C 30 will be listed.

Target lesion details including lesion type, lesion sub-type, size (largest and smallest diameter), location, distance from pleura, and shape will be summarized with statistics appropriate for categorical or continuous variables. Non-target lesion data will be listed. Selected information from the ablation procedure (duration of procedure, duration of ablation delivery, type of anesthesia, maximum power applied, and maximum temperature observed) will also be summarized with statistics appropriate for categorical or continuous variables.

Summary statistics will be presented for evaluations made by the independent reviewer for selected fields relating to ablation of the target lesion (largest diameter, smallest diameter, lesion location, distance from pleura, ablation margin, technical success, technique efficacy, and target lesion recurrence at any visit). All other target lesion data and all non-target lesion data from the independent reviewer will be listed.

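### SAP 9.4 summarises only three sections of the User Experience Survey, a primary endpoint, for a sample-size reason that does not explain which sections were kept

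*SAP*

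**What the plan says.** Protocol 6.1 lists three primary endpoints and names this one first: "Device user experience: The data will come from the User Experience Survey, which will be completed by the treating physician following each ablation procedure". For its analysis, protocol 10.9 makes a commitment without exceptions: "Summary statistics will be provided for each question".

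The opening text of the SAP reports that, after a subject's death and a DSMB meeting, "the decision was made to permanently stop study enrollment and follow the 10 previously-enrolled subjects". SAP section 7 confirms that "enrollment was stopped after 10 subjects received ablation and the original planned target of 40 subjects was not achieved".

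SAP 9.4 then restates the protocol commitment and departs from it: "given the overall reduced sample size, only responses to the Probe Placement, Ablation Procedure, and General System Feedback sections will be summarized". It adds that everything collected on the survey will be listed, which is Listing 24 in the appendix. It does not name the sections left out and does not say why these three were kept.

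Elsewhere the SAP treats the exploratory quality-of-life data in two ways. SAP 9.7 says "Responses to each question of the EORTC QLQ-LC 13 will be summarized at each visit where the questionnaire was administered", and the next sentence reduces the QLQ-C30 to a listing. SAP 9.5 also reduces the primary and secondary efficacy rates and the readmission data to listings, again citing the smaller sample.

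**The concern.** A primary endpoint is to be summarised in part, and the parts were chosen after enrolment had ended. The study is open-label (SAP section 3), and the survey is completed after each procedure. Responses from the initial ablations could therefore have existed when the SAP text was written. When the content of a primary summary is fixed at that stage without a stated rule, a reader cannot exclude that the content of the answers played a role, whatever the intent.

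The survey is meant to show the sponsor whether and where the device needs enhancement (protocol 5.1). A difficulty reported in an omitted section would appear only in a by-subject listing and in no summary table. From the SAP alone, a reader cannot tell which topics those are.

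**Working it through.** **Inputs**

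- Planned sample size: 40. SAP section 7 says only that "a target sample size of 40 subjects (with an approximate equal distribution of device use by interventional pulmonologists and thoracic surgeons) was deemed adequate".
- Achieved: 10 ablated (SAP section 7).
- Inference: "No hypotheses are specified for this study and no p-values are being calculated" (SAP section 5).
- Survey analysis: every question (protocol 10.9) against three sections (SAP 9.4).
- Table shells: SAP appendix, Tables 9, 10, 11 and 13.

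**Step 1. Is there a threshold that 10 fails to meet?** The 40 has no hypothesis, power or precision target behind it, so there is no figure to reproduce and no minimum n from which a tabulation becomes valid.

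**Step 2. What does the smaller n cost?** A reported percentage moves in steps of 1/n: 1/10 = 10 points instead of 1/40 = 2.5 points. If intervals were wanted, the exact (Clopper-Pearson) 95% limits are the 0.025 quantile of Beta(x, n − x + 1) and the 0.975 quantile of Beta(x + 1, n − x).

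| Observed | n = 10: 95% CI (width) | n = 40: 95% CI (width) |
|---|---|---|
| 50% | 18.7% to 81.3% (62.6 points) | 33.8% to 66.2% (32.4 points) |
| 80% | 44.4% to 97.5% (53.1 points) | 64.4% to 91.0% (26.6 points) |
| 90% | 55.5% to 99.8% (44.3 points) | 76.3% to 97.2% (20.9 points) |

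The intervals roughly double in width. Table 9, however, gives no interval for any survey item. It shows counts and percentages, or n, mean, SD, median and range. The loss of precision therefore does not touch the planned output.

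**Step 3. Can n distinguish one section from another?** Each procedure yields one survey, so the number of surveys is the same for every section. A reason that applies equally to all sections cannot select three of them. If an omitted section applied to only some procedures, or was often left blank, that would be a separate reason, and the SAP does not give it.

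**Step 4. Does the SAP treat n = 10 as a bar to tabulation?** Counts from the shells:

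- Table 9, survey: 10 items (2 yes/no, 3 continuous, 5 on a five-point scale), each reported once.
- Table 13, QLQ-LC13: 14 questions × 6 visits = 84 distributions.
- Table 10, pulmonary function: 17 parameters × 5 columns = 85 blocks.
- Table 11, hematology: 15 parameters × 4 visits = 60 blocks.
- QLQ-C30: no summary table.

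The fair comparison per administration is 14 QLQ-LC13 questions against 10 retained survey items plus an unknown number omitted. The figure of 84 shows only that table volume was not treated as a limit. It does not show that the survey is the shorter instrument.

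**Step 5. What cannot be computed.** Protocol 5.1 says the survey is a separate document. The number of omitted questions, their type and their content are therefore unknown.

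**The case against.** The best defence is that this is open, general descoping. SAP 9.4 states the commitment, the departure and the reason together, and all responses are listed. SAP 9.1 counts listings as part of the planned output, and a listing for 10 subjects is short. Other analyses were cut harder: the Per Protocol set and the Kaplan-Meier analysis are gone, and the efficacy rates, readmission and QLQ-C30 are listed only. Table 9 keeps core usability items, including whether the system is predictable and simple to use, so unfavourable answers there would be tabulated. Table 7 adds procedure time, ablation time and probe repositions. With no test planned, no inferential conclusion can shift.

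Most of this stands, and it limits the weight of the point. It does not answer the narrower question of why these three sections were kept. Disclosure gives a reason, but the reason does not separate the kept sections from the dropped ones, and the dropped ones are not identified. The harder cuts in SAP 9.5 concern secondary endpoints. This one is primary and is reported in part.

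A reader might infer three stronger things that the documents do not support:

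- **That the endpoint itself was cut.** Only its summary was reduced; the data are listed.
- **That exploratory questionnaires, being longer, were all spared.** Only the QLQ-LC13 keeps a full summary. The QLQ-C30 lost its summary entirely, although protocol 10.9 planned one. Relative length cannot be judged without the survey.
- **That sections were chosen with knowledge of the answers.** Nothing says so. SAP 9.8 reports no formal interim analysis beyond the DSMB reviews, and protocol 10.1 requires only that the SAP be final before database lock.

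**Conclusion.** The point holds as an unexplained selection within a primary endpoint, made after enrolment stopped. Protocol 10.9 promises all questions and SAP 9.4 delivers three sections. The stated reason neither prevents a descriptive table nor explains the choice. The result is an avoidable risk of selective reporting, not evidence that it occurred.

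Severity is minor to moderate. The study's validity is not affected, no interval or test changes, and the data remain visible in a listing. The conclusion assumes that each survey was offered in full, so that n is common to all sections. It also assumes that the omitted sections hold at least some items that can be tabulated. The documents confirm neither, because the survey is not part of them. If the omitted sections were free text only, listing them would be adequate and the remaining defect would be that the SAP does not say so.

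**What to change.** In SAP 9.4 and Table 9, summarise every survey question as protocol 10.9 states: counts and percentages for categorical items; n, mean, SD, median and range for continuous items; free text listed. If a short main table is preferred, keep Table 9 and put the other sections in a second table.

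If the sponsor still wants to leave sections out, SAP 9.4 should name them, give a reason that does not depend on n, and state whether survey responses had been reviewed when the choice was made. That is a weaker remedy than tabulating everything.

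The cost is a few more rows in Table 9, or one more table, programmed from data already in Listing 24. No new data are needed.

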9.5 Secondary Endpoint Analyses

The study protocol indicates that summaries will be provided for the primary and secondary efficacy rates as well as hospital readmission rates. However, data relevant to these endpoints will only be listed given the reduction in overall sample size. The number and percentage of subjects experiencing target lesion recurrence at any time during following will be summarized and an exact 95% confidence interval will be estimated, but the Kaplan-Meier analysis described in the study protocol will not be performed.

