Primary endpoints	
 • Device user experience: The data will come from the User Experience Survey, which will be completed by the treating physician following each ablation procedure. • Technical success, defined as: ablation of the target lesion according to the protocol and covered completely, with an adequate margin, as defined by the performing physician (that is, the ablation zone completely overlaps or encompasses the target lesion plus an ablative margin), as assessed by cone beam CT imaging, immediately following the procedure. • Technique efficacy, defined as: ablation of the target lesion according to the protocol and covered completely, with an adequate margin, as defined by the performing physician (that is, the ablation zone completely overlaps or encompasses the target lesion plus an ablative margin), as assessed using CT imaging at Visit 3, which is 30 days \pm 7 days after the first ablation procedure.

Secondary endpoints
	
The secondary endpoints, include the following:
 
 • Any complications attributable to the procedure, including all device-related, procedure-related, and SAEs, evaluated from the start of ablation through 30 days ± 7 days post-ablation and from the start of ablation through end of follow-up (1-year post-ablation) or early discontinuation. • Primary efficacy rate, defined as: the percentage of target soft tissue lesions successfully eradicated following the first ablation procedure, as assessed using CT imaging. • Secondary efficacy rate, defined as: the percentage of soft tissue lesions that have undergone successful repeat ablation following identification of local soft tissue lesion progression, as assessed using CT imaging. • Target lesion recurrence, defined as reappearance of the lesion at the treated site, as assessed using CT imaging. • LOS, measured from post-ablation to discharge. • Hospital readmission rate, defined as any readmission to the hospital within 30 days.

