6.2 Secondary Endpoints

The secondary endpoints include the following:

- Any complications attributable to the procedure, including all device-related, procedure-related, and serious adverse events (SAEs), evaluated from the start of ablation through 30 days \pm 7 days post application of ablation and from the start of ablation through end of follow-up (1-year post-ablation) or early discontinuation.
- Primary efficacy rate, defined as the percentage of target soft tissue lesions successfully eradicated following the ablation procedure, as assessed using CT imaging.
- Secondary efficacy rate, defined as the percentage of soft tissue lesions that have undergone successful repeat ablation following identification of local soft tissue lesion progression, as assessed using CT imaging.
- Target lesion recurrence, defined as reappearance of the lesion at the treated site, as assessed using CT imaging.
- Length of stay, measured from after the ablation procedure until the patient is discharged home.
- Hospital readmission rate, defined as any readmission to the hospital within 30 days.

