1.1 Study Objectives

The primary objective of the study was to evaluate the NeuWave Flex Microwave Ablation System in transbronchial ablation procedures for adult subjects with a medically inoperable primary soft tissue lesion, based on the following assessments:

- a. Device user experience survey
- b. Technical success
- c. Technique efficacy

Device user experience was collected from the treating physician who completed the User Experience Survey following each ablation procedure throughout the study, when applicable. The survey focused on procedure workflow and the user's assessment on ease/difficulty of using the device. The device user experience was designed to augment the Product Development Specialist's understanding of the usability of the Flex system and determine which enhancements, if any, are needed.

The secondary objectives were the following:

1. To evaluate safety through the monitoring of device-related and procedure-related adverse events (AEs) and all serious adverse events (SAEs), from start of ablation through 1-year post-ablation.
2. To establish device and procedure effectiveness by following subjects for 1-year post-ablation to ensure completeness and durability of treatment effect, based on standard endpoints in microwave ablation, as follows:
 - a. Primary efficacy rate
 - b. Secondary efficacy rate
 - c. Local soft lesion recurrence

- d. Length of hospital stay, measured from post-ablation to discharge
 - e. Hospital readmission rate.
3. To calculate hospital readmission rate, defined as any readmission to the hospital within 30 days of the first ablation procedure (Visit 2A).

The exploratory objectives were the following:

- 1. To assess the quality of life post microwave ablation of the lung throughout the 1 year \pm 1 month follow-up period.
- 2. To assess the level of pain during the initial 30 days \pm 7 days post-ablation.

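### SAP 9.5 reduces the primary efficacy rate to a listing because of sample size, although three other rates keep exact intervals on the same 10 subjects, so eradication after the first ablation has no estimate

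*SAP*

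**What the plan says.** Protocol 10.9 first specifies a number, percentage and 95% confidence interval for technical success, and then extends that treatment to other rates: "Technique efficacy, as well as primary and secondary efficacy rates and hospital readmission rates, will be summarized in a similar manner".

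The synopsis defines the primary efficacy rate as "the percentage of target soft tissue lesions successfully eradicated following the first ablation procedure", judged on CT. Protocol 6.2 gives nearly the same definition without the word 'first': "Primary efficacy rate, defined as the percentage of target soft tissue lesions successfully eradicated following the ablation procedure, as assessed using CT imaging". Neither gives an assessment visit or a criterion for eradication. The secondary efficacy rate is "the percentage of soft tissue lesions that have undergone successful repeat ablation following identification of local soft tissue lesion progression".

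SAP Section 7 records that "enrollment was stopped after 10 subjects received ablation and the original planned target of 40 subjects was not achieved". SAP 9.5 acknowledges the protocol's plan for the primary efficacy, secondary efficacy and readmission rates and then changes it: "However, data relevant to these endpoints will only be listed given the reduction in overall sample size". The same paragraph keeps a count, percentage and exact 95% interval for target lesion recurrence. SAP 9.4 keeps them for technical success and technique efficacy.

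SAP 1.1 still records the second secondary objective, "To establish device and procedure effectiveness by following subjects for 1-year post-ablation to ensure completeness and durability of treatment effect", with the primary efficacy rate as item a. The SAP appendix says its shells cover every summary to be produced. None of Tables 1 to 22 has a row for either efficacy rate, and no listing title names one.

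**The concern.** The reason given for dropping the primary efficacy rate applies equally to rates that were kept. A proportion out of 10 needs no minimum sample to be reported with an exact interval, and the SAP accepts that for three other proportions. SAP 9.1 also says that descriptive analyses will be provided for the pre-specified endpoints, and 9.5 departs from this.

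At stake is the completeness part of the effectiveness objective. The study report would not say what share of target lesions was eradicated by the first ablation. A reader working from the listings would have to choose a visit and a rule, and two readers could reach different rates.

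**Working it through.** **1. Is there a figure to reproduce?** No. The target of 40 was judged adequate without a calculation, and SAP Section 5 specifies no hypothesis or significance level. The relevant arithmetic is the exact 95% interval, which is the SAP's own method for its other proportions.

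**2. Denominator.** Under inclusion criterion 6 (Protocol 7.3), only one qualifying lesion may be treated on the day of ablation. Ten ablated subjects therefore give at most 10 target lesions, the same maximum as for the three retained rates.

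**3. Formula.** For x successes in n (Clopper-Pearson), the lower limit is the 0.025 quantile of Beta(x, n − x + 1) and the upper limit is the 0.975 quantile of Beta(x + 1, n − x). When x = n the lower limit reduces to 0.025^(1/n) and the upper limit is 100%. For 10/10 this gives 0.025^(1/10) = 0.692.

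**4. Results.** The documents give no efficacy rate, so a range of outcomes is shown.

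| Outcome | Exact 95% interval |
|---|---|
| 10/10 | 69.2% to 100% |
| 9/10 | 55.5% to 99.7% |
| 8/10 | 44.4% to 97.5% |
| 7/10 | 34.8% to 93.3% |
| 5/10 | 18.7% to 81.3% |
| 9/9 (one subject not evaluable) | 66.4% to 100% |
| 40/40 (planned N) | 91.2% to 100% |
| 36/40 (planned N) | 76.3% to 97.2% |

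At N = 10 the width runs from 30.8 points (10/10) to 62.6 points (5/10). For the same count out of 10, these are exactly the intervals the SAP will print for technical success, technique efficacy and recurrence.

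**5. Secondary efficacy rate.** Its denominator is only the lesions that progressed locally and were ablated again, and this could be zero. Assuming one to three such lesions, all successful, the lower limits are 2.5% (1/1), 15.8% (2/2) and 29.2% (3/3). These intervals carry almost no information.

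**6. Do the retained rates stand in for eradication?**

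| Rate | What it measures | When | In SAP tables |
|---|---|---|---|
| Technical success | Ablation zone covers lesion plus margin, cone beam CT | Immediately after the procedure | Tables 6 and 22 |
| Technique efficacy | The same coverage, on CT | Day 30 | Tables 8 and 22 |
| Target lesion recurrence | Lesion reappears at the treated site, on CT | Day 30 to Month 12 | Tables 8 and 22 |
| Primary efficacy rate | Target lesion eradicated by the (first) ablation, on CT | Not stated | None |

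Read literally, a lesion that was never eradicated cannot reappear. It could count as no recurrence while being a primary efficacy failure, so a low recurrence rate does not imply a high eradication rate.

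**The case against.** The strongest reply is that the SAP is open about the change, that the study is descriptive, and that the underlying data are not lost. All collected fields will be listed, including target lesion details from the site and the central reviewer (Listings 18 and 20) and the ablation procedure (Listing 22). Technique efficacy and recurrence keep exact intervals, so completeness and durability are not left without any estimate. All of this is correct. It limits the point to one named rate, but it does not supply that rate.

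The objection also stands in full for the secondary efficacy rate, where a very small or empty denominator makes sample size a fair reason.

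Three stronger readings are tempting, and the documents do not support them.

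- **Selective reporting.** A reader might infer that eradication was dropped because of its results, since the SAP was written after enrolment stopped in an open-label study. The same SAP also drops the Per Protocol set, the Kaplan-Meier analysis, the readmission summary, parts of the user survey summary and the QLQ-C30 summary. That pattern fits general downsizing. The rate kept, recurrence, records treatment failure and is also summarised from the independent reviewer. Nothing shows that results drove the choice.
- **The rate can simply be tabulated from data in hand.** Protocol 8.2.4 and 8.2.5 record CT lesion details and the number of successful repeat ablations at Months 6 and 12. No eradication field is visible there or among the reviewer's fields named in SAP 9.7. Parts of the protocol text are redacted, so such a field may or may not exist.
- **The SAP claims that effectiveness will be established.** SAP 1.1 is a past-tense record of the protocol's objective. Rewording it would misstate what the protocol set out to do.

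**Conclusion.** The point holds for the primary efficacy rate. A pre-specified count, percentage and interval were replaced by a listing for a reason that does not distinguish this rate from three that were kept on the same subjects. Item a of the effectiveness objective has no estimate as a result, and no retained rate measures it.

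The loss is one rate out of 10 lesions, with an interval between about 31 and 63 points wide if all 10 are evaluable. Even 10/10 would leave true rates just under 70% inside the interval, so the data can describe effectiveness but cannot establish it. No sample size, power or significance level is affected.

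The conclusion assumes one target lesion per subject and, for the N = 10 figures, that all 10 are evaluable. The SAP reports one death without its timing, so a later CT may have fewer. The more basic weakness is that the endpoint has no stated visit or eradication criterion, and that the synopsis and Protocol 6.2 differ on whether it refers to the first ablation.

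**What to change.** - Restore the primary efficacy rate in Table 8, and in Table 22 if the independent reviewer's data allow, as n/N with an exact 95% interval on the Full Analysis Set. Show the number not evaluable.
- State the CT visit or visits used, for example the scheduled Month 6 and Month 12 scans, and the rule that derives eradication from the recorded lesion and repeat-ablation data. If it cannot be derived, say so and why.
- Reconcile the synopsis definition (first ablation) with Protocol 6.2 (the ablation).
- Label the rule as specified after enrolment stopped.
- Report the secondary efficacy rate as a plain n/n count without an interval.
- Leave the objective in SAP 1.1 as it stands. Add a sentence that 10 subjects can only describe effectiveness, citing 69.2% to 100% for 10/10 and 44.4% to 97.5% for 8/10.

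The cost is a few table rows, one derivation rule and one sentence, with no new visits. The downsides are wide intervals and a rule written late in an open-label study, which is why the label is needed.
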